## 13 Assessment of Safety and Data Safety Monitoring Plan (DSMP)

### 13.1 Definitions for Safety Assessment

The following definitions will be used in the assessment of safety:

*Adverse Event (AE)* is any untoward or unfavorable medical occurrence in a human subject, including any abnormal sign (for example, abnormal physical exam or laboratory finding), symptom, or disease, temporally associated with the subject's participation in the research, whether or not considered related to the subject's participation in the research.

*Serious Adverse Event (SAE)* is any adverse event that

- (1) results in death;
- (2) is life-threatening;
- (3) results in inpatient hospitalization or prolongation of existing hospitalization;
- (4) results in a persistent or significant disability/incapacity;
- (5) results in a congenital anomaly/birth defect; or
- (6) based upon appropriate medical judgment, may jeopardize the subject's health and may require medical or surgical intervention to prevent one of the other outcomes listed in this definition (examples of such events include allergic bronchospasm requiring intensive treatment in the emergency room or at home, blood dyscrasias or convulsions that do not result in inpatient hospitalization, or the development of drug dependency or drug abuse).

*Life-threatening* means that the event places the subject at immediate risk of death from the event as it occurred.

*Unanticipated Problem* is defined as an event, experience or outcome that meets **all three** of the following criteria:

- is unexpected; AND
- is related or possibly related to participation in the research; AND
- suggests that the research places subjects or others at a greater risk of harm (including physical, psychological, economic, or social harm) than was previously known or recognized.

*Possibly related* means there is a reasonable possibility that the incident, experience, or outcome may have been caused by the procedures involved in the research

*Unexpected* means the nature, severity, or frequency of the event is not consistent with either:

- the known or foreseeable risk of adverse events associated with the procedures involved in the research that are described in (a) the protocol-related documents, such as the IRB-approved research protocol, any applicable investigator brochure, and the current IRB-approved informed consent document, and (b) other relevant sources of information, such as product labeling and package inserts; or
- the expected natural progression of any underlying disease, disorder, or condition of the subject(s) experiencing the adverse event and the subject's predisposing risk factor profile for the adverse event.

### 13.2 Safety Review

This study is not greater than minimal risk. Unanticipated Problems, Adverse Events, and protocol deviations will be reported to the IRB as required by IRB policies.

### 13.3 Reporting Plans

The Principal Investigator at BMC/BU Medical Campus will report Unanticipated Problems, safety monitors' reports, and Adverse Events to the BMC/BU Medical Center IRB in accordance with IRB policies:

- Unanticipated Problems occurring at BMC/BU Medical Campus will be reported to the BMC/BU Medical Campus IRB within 7 days of the investigator learning of the event.
- Adverse Events (including Serious Adverse Events) will be reported in summary at the time of continuing review, along with a statement that the pattern of adverse events, in total, does not suggest that the research places subjects or others at a greater risk of harm than was previously known.

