#### 4.2.3 Exploratory Outcome Measures

Changes in patterns of healthcare utilization is assessed via chart review from 6 months pre-treatment to 6 months post-treatment. We extract variables from the medical record including number of visits, visit types/departments, no-shows, etc. to characterize healthcare utilization.

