In the case that suicidality is indicated during the participant's sessions with an IBH clinicians, the IBH clinician will follow the standard safety procedures used in IBH. This process involves clinician assessment of patient safety and negotiating appropriate follow-up care for the patient (including but not limited to: paging the Integrated Behavioral Health team, scheduling a followup visit, referral to outpatient psychiatry, calling the BEST hotline, sending patient to the emergency department). IBH clinicians will report any safety assessments and treatment followup plans related to patients participating in the study to the study team. The suicidality protocol (Psychiatric Emergencies) is the same for all conditions. Specifically, a person could disclose thoughts of harm to self or others in the context of a clinical appointment, through study measures, or during a study visit or check-in with study staff. Participants are not able to disclose this information during webSTAIR sessions because only the user has access to item-level information. We will inform participants in all conditions to reach out to their clinicians, the study team, call 911, and/or present to the ED if they are having a psychiatric emergency.

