### *Web-administered STAIR (webSTAIR)*

Participants randomized to webSTAIR complete the program at their own pace. WebSTAIR includes the same content as Brief STAIR in ten online modules, which include audio, video, and text delivery of psychoeducation and therapy components, with interactive exercises to assist in skills practice. All webSTAIR participants will have a therapist on record for treatment oversight (in case higher-level of care is needed) and for treatment planning purposes. In some cases, webSTAIR participants will have access to their study therapists for sessions outside of this treatment, i.e., support that is not PTSD-specific. This may include regular therapy sessions (which typically occur every 4-6 weeks in usual care), but *not* Brief STAIR or other trauma-focused therapies during the treatment window. The RA provides patients with unique login information, technology support, and lightly encourages engagement through biweekly reminder phone calls/texts. The principal investigator (PI) and RA have access to administrator-level login, which allows them to access behavioral data on participant progress (time spent, modules completed). To protect patient privacy, open text fields within webSTAIR (e.g., personal written answers to exercises and modules) are not viewable by study staff. Patients have access to the program for all 9 months of study participation, though progress is only reported back to study therapists during the active treatment phase (weeks 0-15).

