*Medical Chart Extraction Data:* Participants' medical records will be accessed to obtain information about session scheduling, information about ongoing treatment at BMC, and other healthcare utilization data from 6 months pre-enrollment to 9 months from baseline. Participants will be asked to sign a medical release form in the case that they move out of the area during the study or attend visits at a different hospital, so that we may obtain medical records from their new hospital/doctor. In addition, we will obtain the list of EPIC encounters of each enrolled patient in order to keep track of number of scheduled/attended/no-showed appointments. In total, the following information will be extracted from participant medical records: MRN, Name, DOB, problems lists, and encounter data (date and time of scheduled appointments, and date and time of unscheduled care [i.e., emergency department visits, urgent care visits, Boston Emergency Services Team (BEST) safety evaluations, records of hospitalization]). Participants will be informed of this extraction during the informed consent process.

*Surveys for participants:* Self-report measures that have been shown to have excellent psychometric properties will be used to assess mental health and general well-being for each of the three study assessments (baseline, 15 week, and 9-month). This will include the LEC-5 and PCL-5 to assess trauma exposure (historical at the baseline study visit and any new traumatic events at the post-treatment and follow-up assessments) and current PTSD symptoms; the Difficulties in Emotion Regulation Scale (DERS) to assess emotion regulation; the Interpersonal Support Evaluation List (ISEL-12); the Posttraumatic Cognition Inventory (PTCI-9) to assess cognitions associated with PTSD; and the Brief Symptom Inventory (BSI-18) to assess for general mental health issues. Patients will also complete the Coronavirus Stressor Screener, the Everyday Discrimination Scale (EDS), and the Traumatic Symptoms of Discrimination Scale (TSDS) to understand stress response related to Covid-19 and racism. During the baseline assessment, patients will also be asked to complete a demographic questionnaire to collect

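### The adverse-event summary has its conclusion worded in advance and no view by arm, and charted hospitalisations are not routed to the SAE record

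*Combined protocol and SAP*

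**What the plan says.** All references are to the combined protocol and SAP.

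- **Reporting (13.3).** The timing is set as follows: "Adverse Events (including Serious Adverse Events) will be reported in summary at the time of continuing review". The section also fixes the message that goes with this summary: "along with a statement that the pattern of adverse events, in total, does not suggest that the research places subjects or others". The sentence closes by naming a risk of harm higher than the one already recognised. No alternative wording is given for a pattern that does suggest greater risk. A separate and faster route exists: "Unanticipated Problems occurring at BMC/BU Medical Campus will be reported to the BMC/BU Medical Campus IRB within 7 days", counted from when the investigator hears about the problem.
- **Definition (13.1).** An AE counts whether or not it is thought related to the research. It is an SAE if, among other criteria, it "results in inpatient hospitalization or prolongation of existing hospitalization".
- **Chart data (4.2 and 12).** Records are extracted from 6 months before enrolment to 9 months after baseline. They include emergency and urgent-care visits, "Boston Emergency Services Team (BEST) safety evaluations, records of hospitalization". The stated uses are session scheduling, ongoing treatment and utilization. Section 4.2.3 makes utilization exploratory: "Changes in patterns of healthcare utilization is assessed via chart review". Section 15.3 also uses behavioral health encounter counts as a measure of engagement.
- **Other ways events come to light (6.1 and 8).** A suicide-risk alert on the BSI-18 runs in both arms at baseline, 15 weeks and 9 months. Clinicians in the integrated behavioral health (IBH) practice report safety assessments to the study team. On suicidality, 6.1 adds: "Participants are not able to disclose this information during webSTAIR sessions because only the user has access to item-level information". Section 8 plans five clinician sessions for Brief STAIR. For webSTAIR it plans a therapist on record and biweekly reminder calls or texts from the research assistant, and adds: "In some cases, webSTAIR participants will have access to their study therapists for sessions outside of this treatment".
- **Analysis and stopping (15.3 and 13.4).** The statistical methods name no AE analysis, and there are no stopping rules.

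**The concern.** A safety summary should report what the data show. Here the plan supplies the finding and leaves only the event list to be filled in. A team that follows 13.3 literally has no wording for an unfavourable pattern.

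Two further gaps affect what the summary can show. First, the trial randomises between a clinician-delivered and a self-directed format, and section 12 sets out to compare their relative advantages and disadvantages. Nothing in the plan would show whether harms fell unevenly between them. Second, section 13 defines AEs and SAEs but names no method for finding them. The record that would show admissions in both arms on the same basis is already collected, but for other purposes. An admission could appear in the utilization data and be absent from the SAE summary. The SAE count would then depend on the BSI-18 alert, which covers suicide risk only, and on contact with clinicians or staff, which is planned differently in the two arms.

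**Working it through.** The plan gives no safety figure to reproduce, so the main check sets the text side by side. The arithmetic after it is illustration only.

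**Text check**

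| Question | Where | Finding |
|---|---|---|
| Is the conclusion open? | 13.3 | No. One direction only |
| Is any AE summary by arm planned? | 13.2, 13.3, 15.3 | None named |
| Can an admission be an SAE? | 13.1 | Yes, related or not |
| Are admissions collected in both arms? | 4.2, 12 | Yes, to 9 months |
| Are they sent to the AE record? | 4.2, 4.2.3, 12, 13, 15.3 | Not stated anywhere |

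**Planned contact in weeks 0 to 15 (section 8)**

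- Brief STAIR: 5 planned clinician sessions.
- webSTAIR: no required clinician session. Where usual sessions occur every 4 to 6 weeks, 15/6 = 2.5 to 15/4 = 3.75. Reminders every two weeks give 15/2 = 7.5, so about 7 staff contacts.

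The kind of contact differs between arms. The documents give no detection rate for either kind, so the size of any detection difference cannot be calculated.

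**What a total conceals (30 per arm; event counts assumed)**

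For k events all in one arm, the two-sided Fisher p = 2 × C(30,k)/C(60,k).

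- k = 8: 2 × 5,852,925/2,558,620,845 = 0.005. Split 4 and 4: p = 1.00.
- k = 6: 2 × 593,775/50,063,860 = 0.024. Split 3 and 3: p = 1.00.
- k = 4: 2 × 27,405/487,635 = 0.11. The rates are 4/30 = 13.3% and 0%, pooled 4/60 = 6.7%.

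The total is identical within each of the first two comparisons. The k = 4 case shows that a small imbalance is compatible with chance even when it can be seen.

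**What zero events would mean**

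The one-sided 95% upper bound is 1 − 0.05^(1/n). For n = 60 it is 4.9%, and for n = 30 it is 9.5%. At an assumed true risk of 5%, the chance of seeing at least one event is 1 − 0.95^30 = 79% in one arm and 1 − 0.95^60 = 95% in both together. A clean total says less about either arm than it appears to.

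**What a table by arm can support (two-sided 0.05; all rates assumed)**

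| Risks in the two arms | Pooled | Fisher power, 30 per arm | Approx. n per arm for 80% power |
|---|---|---|---|
| 5% v 10% | 7.5% | 2% | 435 |
| 5% v 15% | 10% | 9% | 141 |
| 5% v 20% | 12.5% | 24% | 76 |
| 5% v 30% | 17.5% | 63% | 36 |
| 10% v 20% | 15% | 10% | 199 |
| 10% v 30% | 20% | 37% | 62 |

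Fisher power was computed exactly; the last column uses the normal approximation. Even a large imbalance is not reliably detected at this size, so the table would be descriptive.

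**The case against.** The strongest reply is that this is a minimal-risk study with working safeguards, and that the sentence in 13.3 may be standard IRB language. An Unanticipated Problem is defined in 13.1 to include unexpected frequency, and its third criterion is close to the wording of the continuing-review statement. A related, unexpected pattern suggesting greater risk therefore has its own 7-day route. Section 13.3 also mentions reports from safety monitors. The trial is unmasked, so the investigator can know the arm of each event, and reporting follows IRB policies that the documents do not reproduce. Safety is neither an outcome in 4.2 nor a hypothesis in 15.1.

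Much of this stands. Individual serious problems are not left without a route, and the absence of stopping rules does not make the continuing-review summary the only look at safety. But these routes work case by case. None produces counts by arm, no section appoints a safety monitor, and the wording still fixes the answer, whatever its origin.

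A reader might infer three stronger things that the documents do not support.

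- **That 13.3 orders the arms to be judged together.** The phrase *in total* describes the pattern of events, and arms are not mentioned. Pooling is inferred from that phrase and from the lack of any summary by arm.
- **That chart extraction is the only source common to both arms, or that its data are used for utilization alone.** The BSI-18 alert runs in both arms, and the chart data also serve scheduling, treatment tracking and engagement.
- **That webSTAIR will be made to look safer.** The five Brief STAIR sessions are planned, but completion is itself an outcome (4.2.1) and patients may change treatment (section 12). webSTAIR participants have reminders and a therapist on record. With no comparison by arm planned, unequal detection does not by itself produce a false contrast. It would matter once events were tabulated by arm, which is why the source of each event should be shown.

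**Conclusion.** The point holds in a limited form, and it is more than missing detail. As written, 13.3 yields a favourable statement whatever the event pattern, no AE summary by arm is planned, and admissions that may meet the SAE definition have no stated path to the SAE count. The possible results are a wrong safety statement and an incomplete SAE count.

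The first part rests on explicit text. The second and third rest on silence across sections 4.2, 12, 13 and 15.3, and IRB policies outside the documents could fill part of the gap. How many events would be missed, and whether detection differs between arms, is unknown. Every event count and event rate used in the illustrations is an assumption. Only hospitalisation matches the SAE definition on its face. An emergency, urgent-care or BEST contact does not qualify by itself.

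**What to change.** 1. **13.3:** replace the fixed statement with an assessment of whether AEs, overall and in each randomised arm, point to a higher risk of harm than was previously recognised.
2. **12 and 13:** state that hospitalisations found in the existing chart extraction are checked against the SAE definition in 13.1, and that those that qualify are entered in the AE record.
3. **Emergency, urgent-care and BEST contacts:** tabulate as counts by arm, and classify as AEs or SAEs only where the available detail shows that they qualify. Section 12 lists only dates and times for these contacts, so classifying all of them would need clinical detail that is not now extracted.
4. **Reporting:** show AEs and SAEs by arm and by source (chart, survey alert, clinician or staff report), with exact confidence intervals and no formal test.

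The cost is revised wording, one descriptive table and a little investigator and research-assistant time to classify events. No change to treatment or safety procedures is involved. Parts of sections 2 and 15.3 are in the past tense. If follow-up is complete, the hospitalisation check and the table by arm can still be done on the extracted records.

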### 13.4 Stopping Rules

The study has no pre-defined stopping rules.

## 14 Data Handling and Record Keeping

### 14.1 Confidentiality

We will make every attempt to protect confidentiality. All participants will be assigned a study ID and questionnaires, and audio files will only have that study ID without other identifiable information. REDCap will be used to enter coded study data. Only coded data will be included in REDCap. Study staff may enter data from paper forms or from patient phone calls into REDCap or participants may complete surveys directly into REDCap. All paper data files will be kept in a locked file cabinet in a locked office. In person and telehealth intervention sessions will be audio-recorded. The recordings will be saved on a password protected BMC network drive that can only be accessed by members of the study team and labeled only with their Study ID. After the recording is saved on the password protected BMC network drive, the recording will be deleted from the audio-recording device. WebSTAIR (operated by the Veteran's Health Administration) is protected by a data security assurance, ensuring that all content is

password-protected, item-level and written content is not viewable outside of an individual account, and all information on the site is maintained in a confidential and secure manner. The VHA is not engaged in the same research project and will not have access to any study data collected by BMC (via RedCAP) for purposes of this study. They will not be able to link data gathered by webSTAIR to our data, as only BMC study team will know the link between webSTAIR usernames and Study ID numbers, and only the BMC study team will have access to data collected during study visits. webSTAIR is a password-protected website. For this study, we have been allocated a set of 30 patient-level accounts (with unique usernames and passwords) to distribute to study participants. In addition, the program manager has created four administrator-level account (2 for BMC study staff, including PI and RA; and 2 for VA collaborators). The administrator-level account allows study staff to see patient engagement information such as the date, time, and duration of accessing various modules on the website and optional self-assessments so patients can track their progress. The website does not collect item-level information (e.g., fillable text boxes within the modules and worksheets), this information is only available to patients via their unique login. The webSTAIR website does not communicate with the EMR. Because we will contact patients over the course of the study and will access patients' medical records, we will record their contact information, their date of birth, and their MRN. One list of names and contact information and Study IDs will be kept on a private password protected BMC network drive separate from any data collection tools and will only be accessible to the study team. All identifiable information will be transmitted, stored, analyzed, or otherwise exist only on HIPAA-compliant electronic systems that meet the standards for protection of PHI established by Boston Medical Center. As an extra layer of protection, we have a Certificate of Confidentiality because this project is NIH-funded.

## 15 Statistical Plan

### 15.1 Study Hypotheses

Hypotheses:

- A. Brief STAIR will lead to significant change PTSD symptoms between baseline and 3 months.
- B. WebSTAIR will lead to significant change PTSD symptoms between baseline and 3 months.
- C. There will be no group differences in change in PTSD across conditions.

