## 2 Protocol Summary

Title:	Implementing a Skills Training Evidence-Based Treatment for Posttraumatic Stress Disorder (ISTEP)
Population:	Adult primary care patients with posttraumatic stress disorder symptoms, N=60
Intervention:	Behavioral health interventions, including web-administered and clinician administered brief Skills Training in Affective and Interpersonal Regulation (STAIR) for PTSD
Objectives:	Hybrid type 1 effectiveness-implementation trial to assess the feasibility, acceptability, and preliminary effectiveness of web-versus clinician-administered brief STAIR (primary outcome: PTSD symptoms, secondary outcome: functioning) while gathering information on implementation of both modalities. Findings will inform a full stepped-care approach to PTSD treatment that spans primary care and specialty care.
Design/Methodology:	60 patients were randomized, 30 in each condition (webSTAIR v. Brief STAIR). Participants completed study survey assessments at baseline (0 weeks), 15 weeks (active treatment), and 9-months post-randomization. To ensure consistency in timing of data collection, assessments are not linked to condition or amount of content completed.
Subject Participation Duration:	9 months

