## 12 Study Procedures

The **standard of care** in Primary Care is to provide options for screening and treating posttraumatic stress disorder (PTSD) and related mental health disorders to all patients. Patients

have several options for mental health treatment, including treatment with Integrated Behavioral Health (IBH) therapists, referral to behavioral health specialists in outpatient psychiatry, or referral to community-based behavioral health clinicians. This treatment is not research and takes place regardless of participation in the research components. Specifically, all embedded IBH therapists that work in Primary Care will have the opportunity to receive training and consultation in the STAIR intervention prior to start of the study and will be able to offer this treatment to any patient, regardless of a patient's decision to participate in research components, as a new standard of care. We will also train additional therapists in outpatient psychiatry at BMC in the intervention in case IBH therapists experience issues with capacity in their caseloads. However, the online, self-paced version of the therapy (webSTAIR) will only be provided to research participants for the time being.

*Clinic population:* IBH provides mental/behavioral health treatment to patients in Primary Care who are experiencing a range of mental/behavioral health disorders and symptoms who would like the option of seeing a therapist for these issues through the Primary Care clinic. The Primary Care team includes Primary Care Providers, Nurses and Nurse Practitioners, Community Health Workers, and IBH therapists. IBH therapists include social workers, psychologists, and trainees receiving supervision.

This project will evaluate the intervention for PTSD that is being used in IBH and use the data to iteratively improve the treatment and to explore how effectively the intervention is working in the primary care clinics. We will compare the relative advantages and disadvantages of the in - person/telehealth and web-administered versions of STAIR to better understand and improve the quality of care in IBH.

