### 15.3 Statistical Methods

Analyses were conducted in SPSS version 29. All continuous outcome variables were evaluated for and met the assumptions of normality (using both the Shapiro-Wilk test and the test statistics for skewness and kurtosis) and homogeneity of variance (using Levene's test; Hahs-Vaughn & Lomax, 2020). Chi-square tests and independent samples t-tests were used to examine differences in study variables between participants assigned to STAIR and webSTAIR conditions. Paired samples t-tests were used to

examine pre to post differences and pre to follow-up differences; effect sizes were calculated using Cohen's d. Participant retention, measured by percent of intervention content completed, did not meet the assumption for normality. To compare differences in engagement between STAIR and webSTAIR, we used the Kruskal-Wallis test, a non-parametric test that does not assume distributions between groups are similar. Linear mixed models with repeated measurements nested within patients were used to examine changes in study outcomes across time points and between groups. We used the restricted maximum likelihood estimator and unstructured covariance matrices for residuals. We examined fixed effects of time, treatment group, and time by treatment group interactions for all study outcomes. In post hoc analyses, we used Spearman's correlations to examine the correlation between engagement and baseline trauma symptoms of discrimination, stigma, and attitudes toward help seeking. Post hoc LMMs examined primary outcomes only (PTSD symptoms, mental health symptoms, and depression symptoms) and included two indicators of engagement, percent of assigned intervention completed and additional contact hours (count of behavioral health encounters documented in the electronic medical records).

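### Hypothesis C predicts no between-arm difference in PTSD change, but the plan names only difference tests and no interval or reading rule, so a non-significant result could not support it

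*Combined protocol and SAP*

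**What the plan says.** Section 15.1 lists three hypotheses. A and B predict change in PTSD symptoms within each arm from baseline to 3 months. C is comparative: "There will be no group differences in change in PTSD across conditions". C names no visit.

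Section 15.3 describes the between-arm analyses in two places. One sentence says: "Chi-square tests and independent samples t-tests were used to examine differences in study variables between participants assigned to STAIR and webSTAIR conditions". It does not say which variables or visits are meant, so it may describe baseline comparisons only. The other concerns the linear mixed models (LMMs): "We examined fixed effects of time, treatment group, and time by treatment group interactions for all study outcomes". The only effect size named is Cohen's d, in the sentence on paired tests for "pre to post differences and pre to follow-up differences; effect sizes were calculated using" that statistic.

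Comparing the formats is a stated aim. The Protocol Summary (section 2) gives the objective as assessing "preliminary effectiveness of web-versus clinician-administered brief STAIR (primary outcome: PTSD symptoms, secondary outcome: functioning"), and section 12 says "We will compare the relative advantages and disadvantages of the in - person/telehealth and web-administered versions of STAIR". On size and status, section 2 says "60 patients were randomized, 30 in each condition" and section 15.3 says "Analyses were conducted in SPSS version 29".

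**The concern.** C predicts equality, and the tests named take equality as the null hypothesis. They can produce evidence against C. Failure to reject is not evidence for it unless it is accompanied by an interval narrow enough to exclude differences that matter, and the plan neither commits to an interval nor says which differences matter.

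At stake is the sentence that will be written about the two formats. If the interaction is non-significant and C is reported as supported, a reader could take the self-directed programme to be as effective for PTSD symptoms as the clinician-led one. Section 2 says the findings will inform a stepped-care approach, so that reading could carry forward. Hypotheses A and B predict change, which a significance test can support. This argument does not touch them or the feasibility outcomes.

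**Working it through.** **The plan's own figure.** Section 15.2 calls a total of 60 adequate, on the basis of a pre/post comparison. It gives no alpha, power, effect size, SD or probability, so the figure cannot be reproduced from the documents, and it was not derived for a between-arm contrast.

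**Which planned analysis addresses C.**
- Time-by-group effect: yes. It compares change between arms.
- Group main effect: no. It does not isolate change.
- Independent t-tests: unclear, because variable and visit are not named.
- Paired tests with Cohen's d: no. They are pre/post and pre/follow-up comparisons.

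**Inputs.** From the documents: 30 per arm. Assumed, because the documents are silent: two-sided alpha 0.05 (0.10 as a check); 24 per arm as a second case, 30 × (1 − 0.20); results in units of the SD of change. With complete data, categorical time and an unstructured covariance, the LMM contrast at one visit equals the difference in mean change, so two-sample formulas apply.

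**Precision.** Half-width of the 95% CI = t(0.975, 2n − 2) × √(2/n).
- n = 30: 2.0017 × √(2/30) = 0.517 SD.
- n = 24: 2.0129 × √(2/24) = 0.581 SD.

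**Chance of a non-significant result when a true difference d exists.** Non-central t, df = 2n − 2, non-centrality d × √(n/2). At n = 30 the non-centrality is 1.16, 1.94 and 3.10 for d = 0.3, 0.5 and 0.8.

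| n per arm | alpha | d = 0.3 | d = 0.5 | d = 0.8 |
|---|---|---|---|---|
| 30 | 0.05 | 79% | 52% | 14% |
| 24 | 0.05 | 83% | 60% | 23% |
| 30 | 0.10 | 69% | 39% | 8% |

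**If the interaction is tested jointly over both follow-up visits.** A two-df Hotelling test on the 15-week and 9-month changes, F(2, 2n − 3), was run with the two change scores correlated 0.3, 0.5 or 0.7, and with the 9-month difference equal to all, half or none of the 15-week difference. At n = 30 and a 15-week difference of 0.5 SD, non-significance ranges from 35% to 63%, and exceeds half in 7 of the 9 scenarios.

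**In PCL-5 points.** SD of change = SD × √(2(1 − ρ)), with assumed SD 12 to 18 and ρ 0.5 to 0.7.
- Narrowest (SD 12, ρ 0.7, n = 30): 9.30 × 0.517 = 4.8 points.
- Widest (SD 18, ρ 0.5, n = 24): 18 × 0.581 = 10.5 points.

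The scale runs from 0 to 80 (section 4.2.1).

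**Would an equivalence test help at this size?** Two one-sided tests at 0.05, true difference 0, normal approximation: power = 2Φ(m/√(2/30) − 1.645) − 1, or 0 if negative. This gives 0%, 23% and 85% at margins m of 0.3, 0.5 and 0.8 SD. The margins are illustrative; the documents give none.

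**The case against.** The strongest reply is that the harm is inferred. Sections 15.1 to 15.3 nowhere say that a non-significant interaction will be reported as support for C. That is right. A reader might infer that the plan intends to accept the null, but the text shows only that reporting and interpretation of C are unspecified and that no other route to a verdict is given.

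A second reply is that the analysis is sound. The planned LMM already estimates the difference, and no finite sample can establish exact equality. This also stands: the defect lies in what the plan commits to report and how it will read it, not in the model.

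A third is proportion. Effectiveness is called preliminary, feasibility and acceptability are also primary (section 4.2.1), the hypotheses in section 5 contain no equality claim, and C rests on one line. A reader might conclude that the trial needs a powered equivalence test or more patients. The documents do not support that for a trial framed this way. But C is one of only three hypotheses in the statistical plan, so it still needs a way of being read.

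A fourth concerns timing. Section 15.3 is in the past tense and reports which variables met normality, so data had been examined when it was written. Rewriting C now would obscure what was predicted. This is a good reason to leave C as it stands and change only how it is reported.

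**Conclusion.** The point holds as a gap in reporting and interpretation. The plan can contradict C but has no stated means of supporting it. At 30 per arm the between-arm estimate would carry a 95% CI half-width of about 0.52 SD of change, and a true 0.5 SD difference would go undetected about half the time (52% at two-sided 0.05). These sizes rest on assumed alpha, retention, SD and correlation. The logical gap does not depend on them.

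The documents do not establish that the investigators will misread a null result, or that the LMM is wrong. Confidence is high for the textual gap and lower for the misreading it invites. It should be fixed, as a modest correction.

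A linked inconsistency needs settling at the same time. A and B use 3 months (about 91 days), while the assessments in sections 2 and 5 fall at 15 weeks (105 days) and 9 months. C, listed with A and B, can reasonably be read as sharing their window, but no assessment is scheduled at 3 months.

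**What to change.** Leave C in section 15.1 as stated. Add to section 15.3, as a dated change:

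> For hypothesis C, the between-arm difference in PCL-5 change from baseline to the 15-week assessment, by randomised arm, will be reported as a single LMM time-by-group contrast with its 95% CI (the 9-month contrast likewise, as secondary). A non-significant p-value will not be read as no difference; we will state only which differences the CI excludes.

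Then:
- Reconcile the 3-month window in A and B with the 15-week assessment, so that A, B and C refer to one visit.
- Make no equivalence claim unless a justified margin was set before results were seen.
- If results have been seen, label the addition a reporting correction, not a pre-specified analysis.

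The cost is a few sentences, with no new data, patients or model. The downside is a less favourable conclusion: with a half-width of about 0.5 to 0.6 SD of change, the report would probably have to say that moderate differences between the formats are not excluded.
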